***Exclusion Criteria***

**2) Target Disease Exceptions**

- a) Presence of other concomitant liver diseases including viral hepatitis, PSC, alcoholic liver disease, Wilson's disease, hemochromatosis, or Gilbert's syndrome.
- b) Prior liver transplantation
- c) Decompensated liver disease defined by the presence or history of any of the following
  - i) MELD score > 15
  - ii) Hepatic encephalopathy
  - iii) Ascites
  - iv) Hepatorenal syndrome or serum creatinine > 2 mg/dL
  - v) Total Bilirubin > 3.0 mg/dL
  - vi) INR > 1.8 unless on anticoagulation such as Coumadin.
- d) Use of immunosuppressants within 6 months of Day 0, including azathioprine, prednisone, prednisolone, budesonide, cyclosporine, tacrolimus, methotrexate, or mycophenolate mofetil.
- e) Use of biologic agents including anti-cell and anti-cytokine therapies within 12 months of Day 0.
- f) History of tuberculosis or positive PPD skin test.
- g) Positive hepatitis B surface antigen
- h) Presence of hepatitis C RNA
- i) QT or QTc interval > 500 milliseconds

**3) Medical History and Concurrent Diseases**

- a) Subjects who are impaired, incapacitated, or incapable of completing study-related assessments.
- b) Subjects with current symptoms of severe, progressive, or uncontrolled renal, hepatic, hematologic, gastrointestinal, pulmonary, cardiac, neurologic, or cerebral disease, whether or not related to RA and which, in the opinion of the investigator, might place a subject at unacceptable risk for participation in the study.
- c) Subjects with a history of cancer in the last 5 years, other than non-melanoma skin cell cancers cured by local resection or carcinoma in situ. Existing non-melanoma skin cell cancers should be removed, the lesion site healed, and residual cancer ruled out before administration of the study drug.
- d) Subjects who currently abuse drugs or alcohol.
- e) Subjects with evidence (as assessed by the investigator) of active or latent bacterial or viral infections at the time of potential enrollment, including subjects

**PROTOCOL TITLE: ABATACEPT FOR THE TREATMENT OF PRIMARY  
BILIARY CIRRHOSIS WITH AN INCOMPLETE BIOCHEMICAL RESPONSE TO  
URSODEOXYCHOLIC ACID**

with evidence of human immunodeficiency virus (HIV) detected during screening.

- f) Subjects with herpes zoster or cytomegalovirus (CMV) that resolved less than 2 months before the informed consent document was signed.
- g) Subjects who have received any live vaccines within 3 months of the anticipated first dose of study medication.
- h) Subjects with any serious bacterial infection within the last 3 months, unless treated and resolved with antibiotics, or any chronic bacterial infection (eg, chronic pyelonephritis, osteomyelitis, or bronchiectasis).
- i) Subjects at risk for tuberculosis (TB). Specifically excluded from this study will be subjects with a history of active TB within the last 3 years, even if it was treated; a history of active TB greater than 3 years ago, unless there is documentation that the prior anti-TB treatment was appropriate in duration and type; current clinical, radiographic, or laboratory evidence of active TB; and latent TB that was not successfully treated ( $\geq 4$  weeks).

**4) Physical and Laboratory Test Findings**

- a) Subjects with any of the following laboratory values
  - i) Hemoglobin  $< 8.5$  g/dL
  - ii) WBC  $< 3000/\text{mm}^3$  ( $< 3 \times 10^9/\text{L}$ )
  - iii) Platelets  $< 75,000/\text{mm}^3$  ( $< 3 \times 10^9/\text{L}$ )
  - iv) Serum creatinine  $> 2$  times the ULN
  - v) Serum ALT or AST  $> 5$  times the ULN
- b) Any other laboratory test results that, in the opinion of the investigator, might place a subject at unacceptable risk for participation in the study.

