**7) Other Exclusion Criteria**

- f) Prisoners or subjects who are involuntarily incarcerated.
- g) Subjects who are compulsorily detained for treatment of either a psychiatric or physical (eg, infectious disease) illness.

Eligibility criteria for this study have been carefully considered to ensure the safety of the study subjects and to ensure that the results of the study can be used. It is imperative that subjects fully meet all eligibility criteria.

PROTOCOL TITLE: ABATACEPT FOR THE TREATMENT OF PRIMARY BILIARY CIRRHOSIS WITH AN INCOMPLETE BIOCHEMICAL RESPONSE TO URSODEOXYCHOLIC ACID

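### The platelet exclusion limit is printed in two units that differ 25-fold: 75,000/mm³ is 75 × 10⁹/L, but the bracket gives 3 × 10⁹/L

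*Combined protocol and SAP*

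**What the plan says.** The combined protocol and SAP lists laboratory exclusions in section 6, Exclusion Criteria, under 4) Physical and Laboratory Test Findings. A subject with any one of the listed values is excluded. Two of the lines give a cell count per mm³, followed by a bracket per litre:

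- Item a(ii), white cells: "WBC $< 3000/\text{mm}^3$ ( $< 3 \times 10^9/\text{L".
- Item a(iii), platelets: "Platelets $< 75,000/\text{mm}^3$ ( $< 3 \times 10^9/\text{L".

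(Both quotes stop just before the closing bracket.) Item b adds a discretionary exclusion: "Any other laboratory test results that, in the opinion of the investigator, might place a subject at unacceptable risk". The Exclusion Criteria close, at the end of 7) Other Exclusion Criteria, with the statement "It is imperative that subjects fully meet all eligibility criteria".

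No other part of the documents reviewed gives a platelet limit. The definition of decompensated liver disease, under 2) Target Disease Exceptions, uses the MELD score, encephalopathy, ascites, hepatorenal syndrome or creatinine, bilirubin and INR, but not platelets.

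**The concern.** A limit printed in two units should be the same limit. Here two different per-mm³ limits, 3,000 for white cells and 75,000 for platelets, carry the same per-litre value. They cannot both be right.

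What is at stake is a safety exclusion in a disease that can end in cirrhosis. If a screening form or checklist were built from the per-litre figure, it would admit subjects whom the per-mm³ figure excludes. The documents do not show that any form uses the per-litre figure, and they do not say which unit the local laboratory reports, so this is a possibility and not an observed failure. Since this item alone sets the platelet cut-off, nothing elsewhere in the text corrects it.

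**Working it through.** **Inputs**, all from items a(ii) and a(iii):

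- White cells: 3,000/mm³, bracket 3 × 10⁹/L.
- Platelets: 75,000/mm³, bracket 3 × 10⁹/L.
- Conversion: 1 L = 10⁶ mm³, so count per litre = count per mm³ × 10⁶.

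**Step 1. Reproduce the line that is right.** White cells: 3,000 × 10⁶ = 3 × 10⁹/L. This matches the bracket, so the conversion factor is the one the protocol itself uses.

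**Step 2. Apply the same factor to platelets.** 75,000 × 10⁶ = 75 × 10⁹/L. The bracket prints 3 × 10⁹/L, so it is not reproduced.

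**Step 3. Convert the printed bracket back.** 3 × 10⁹ / 10⁶ = 3,000/mm³.

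**Step 4. Size of the disagreement.** 75 / 3 = 25.

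**Step 5. Range on which the two limits disagree.**

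| Platelet count (× 10⁹/L) | By the per-mm³ figure | By the bracket |
|---|---|---|
| below 3 | excluded | excluded |
| 3 to just under 75 | excluded | not excluded |
| 75 and above | not excluded | not excluded |

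The middle row covers (75 − 3) / 75 = 72 / 75 = 96% of the numeric range below the intended limit. This is a share of a number line and not of patients; the documents give no platelet distribution, so the number of candidates affected cannot be estimated.

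**Step 6. Effect on the design.** None. The figures under Sample Size Determination do not depend on this limit, and they reproduce. With 20 subjects and success defined as 4 or more responders, the probability of 3 or fewer responses at a 5% rate is 0.984 (stated as above 98%), and the probability of 4 or more at a 30% rate is 0.893 (stated as 89%).

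**The case against.** The strongest reply is that this is a typographical slip with no realistic route to harm.

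- **The leading figure governs.** The bracket only restates it. The two limits are also nested: any count below 3 × 10⁹/L is also below 75,000/mm³, so a reader who applies both figures excludes everyone below 75,000/mm³. A subject is wrongly admitted only if someone ignores the first figure and uses the bracket alone.
- **The slip is easy to spot.** Its likely source is one line above.
- **The setting is small.** This is a single-center study of up to 20 subjects, with eligibility decided by the principal investigator or, in that person's absence, a co-investigator. There is no chain of sites across which readings could drift.
- **The 96% figure can mislead.** It describes a numeric range and says nothing about patients.

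All of this stands as an argument about weight, and it is why the practical risk is rated low. None of it makes the bracket correct.

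The discretionary exclusion in item b is a weaker safeguard than it first appears. It covers laboratory results other than those already listed, so whether it reaches a platelet count, which has its own line, is arguable. The closing statement that all criteria must be met is general. It does not turn the bracket into a separate criterion, but it is a fair reason for each numeric limit to have a single value.

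**Conclusion.** The concern holds. The per-litre platelet limit is wrong as printed and is 25 times too permissive: 3 × 10⁹/L where 75 × 10⁹/L is meant.

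The mismatch rests only on the unit conversion and the two printed lines. Two further statements are inferences: that 75,000/mm³ is the intended limit (it is printed first, and a limit of 3,000/mm³ would exclude almost nobody), and that the bracket was copied from the white-cell line. Both lines are complete and legible, so nothing points to a fault in reading the PDF.

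The correction should be made because the error sits in a working safety criterion and not in background text. The practical risk is low, and there is no consequence for the primary endpoint, the sample size or any planned test.

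**What to change.** In item a(iii), change the bracket to < 75 × 10⁹/L. Leave the 75,000/mm³ limit and the white-cell line unchanged. If a screening checklist or case report form was built from this list, check that it carries 75 × 10⁹/L.

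The cost is one corrected figure, with no change to data collection, sample size or analysis.

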**5) Allergies and Adverse Drug Reactions**

- c) Any prior adverse reaction to abatacept.

**6) Prohibited Treatments and/or Therapies**

- d) Subjects who have at any time received treatment with any investigational drug within 28 days (or less than 5 terminal half-lives of elimination) of the Day 1 dose.
- e) Any concomitant biologic DMARD, such as anakinra.

**7) Other Exclusion Criteria**

- f) Prisoners or subjects who are involuntarily incarcerated.
- g) Subjects who are compulsorily detained for treatment of either a psychiatric or physical (eg, infectious disease) illness.

Eligibility criteria for this study have been carefully considered to ensure the safety of the study subjects and to ensure that the results of the study can be used. It is imperative that subjects fully meet all eligibility criteria.

PROTOCOL TITLE: ABATACEPT FOR THE TREATMENT OF PRIMARY BILIARY CIRRHOSIS WITH AN INCOMPLETE BIOCHEMICAL RESPONSE TO URSODEOXYCHOLIC ACID

**7) Number of Subjects**

*a) Study- Wide/Local:*

Up to 20 subjects with PBC will be enrolled in this trial.

**8) Recruitment Methods**

*a) Local:*

Patients will be recruited by direct person to person contact within the GI/Hepatology clinic when the potential patients come in for routine care.

If, during their normal visit, it is noted they may qualify for a clinical trial, they will be approached by the investigator.

The principal investigator is also heavily involved in the PBC patient support groups of Northern California and will recruit potential subjects verbally from these groups as well during normal scheduled presentations.

Patients may also be recruited using recruitment materials such as flyers, posters and social media ads.

*b) HIPAA:*

We are requesting HIPAA waiver:

- Study personnel will be accessing patients' medical records for their Standard of Care when it may become evident that a patient may qualify for the research.
- Access to PHI is necessary to confirm eligibility
- PHI will only be used to assess eligibility and will not be copied or stored anywhere.
- The protected health information will not be inappropriately reused or disclosed to any other person or entity.
- PHI accessed may include, but are not limited to past/current diagnoses and lab results.

## 10) Study Timelines

*Describe:*

- The treatment phase of the study will last 24 weeks with an off-treatment follow up at Week 36.
- We anticipate enrollment to be complete after one year.
- We anticipate primary analysis to be complete after two years.

## 11) Study Endpoints

The primary endpoint assessment will be the biochemical response rate defined by normalization of alkaline phosphatase or decrease of alkaline phosphatase by > 40% of the Day 0 level at 24 weeks of treatment.

Secondary endpoints will include:

- Absolute and percent change in alkaline phosphatase from Day 0 to 24 weeks.
- Absolute and percent change in alanine transferase (ALT) from Day 0 to 24 weeks.
- Change in liver stiffness from Day 0 to week 24 as measured by magnetic resonance elastography.
- Change in quality of life measured by change in PBC-40 from Day 0 to week 24.
- Change in AMA titer from Day 0 to week 24
- Change in IgM level from Day 0 to week 24
- Change in CD4+CD44+CD62L- and CD8+CD44+CD62L- frequencies in PBMC from Day 0 to week 24
- Comparisons of safety assessments pre-treatment, on-treatment, and post-treatment including adverse events, laboratory observations, and physical exam findings.
- Trough concentrations of abatacept concentrations from Week 0 to Week 24
- Immunogenicity evaluated over time by measuring anti-abatacept antibodies and anti-CTLA-4-T antibodies

PROTOCOL TITLE: ABATACEPT FOR THE TREATMENT OF PRIMARY BILIARY CIRRHOSIS WITH AN INCOMPLETE BIOCHEMICAL RESPONSE TO URSDODEOXYCHOLIC ACID

## 12) Procedures Involved

This is an open label, active treatment trial to assess the efficacy and safety of abatacept in subject with PBC who have had an incomplete biochemical response to UDCA.

In this trial, 20 subjects with PBC who have had an incomplete biochemical response to UDCA will be assigned to treatment with weekly subcutaneous injections of 125 mg of abatacept.

The treatment phase of the study will last 24 weeks with an off-treatment follow up at Week 36.

All subjects will undergo blood chemistry panel, complete blood count, INR, AMA, magnetic resonance elastography (MRE), and PBC-40 survey prior to the first dose of study drug. Baseline Mayo Risk Score and MELD score will be calculated from baseline lab values. Subjects will complete the 24 week treatment course and undergo repeat MRE and laboratory testing. Laboratory testing and assessments for adverse events will be conducted at Weeks 2, 4, 12, 24, and 36. Details are given in the Time and Events Schedule.

**Figure 1. Study Design Schematic**

Screening	Abatacept 125 mg SC				Off-Treatment FU	
Week	0	2	4	12	24	36

PROTOCOL TITLE: ABATACEPT FOR THE TREATMENT OF PRIMARY BILIARY CIRRHOSIS WITH AN INCOMPLETE BIOCHEMICAL RESPONSE TO URSODEOXYCHOLIC ACID

Time and Events Schedule for Protocol [IM101-457]

Procedures	Pre-Treatment Visit	Treatment Day 1	Treatment Week 2	Treatment Week 4	Treatment Week 12	Treatment Week 24	Post-Treatment Week 36 
Eligibility Assessments							
Informed Consent	X						
Inclusion/Exclusion	X						
Medical History							
Safety Assessments							
Physical Exam	X					X	
Vital signs	X	X	X	X	X	X	X
Signs and Symptoms		X	X	X	X	X	X
Adverse Events		X	X	X	X	X	X
ECG	X						
PPD	X						
HCV antibody	X						
HBs antigen	X						
HIV antibody	X						
UPT 	X	X		X	X	X	
Efficacy Assessments							
CMP	X	X	X	X	X	X	X
CBC	X	X	X	X	X	X	X
INR	X	X	X	X	X	X	X
CRP	X			X	X	X	X
AMA	X	X	X	X	X	X	X
IgG, IgM, IgA	X	X	X	X	X	X	X
ANA	X	X	X	X	X	X	X
Lipid Panel	X				X	X	X
MR Elastography	X					X	
PBC-40	X					X	
CD44+CD62L-	X				X	X	X
PK/IMG Samples 		X		X	X	X	X
Clinical Drug Supplies							
Abatacept 125 mg SC once weekly		X	X	X	X	X	

 Also to be performed for any subjects discontinuing the study with documentation for reason for discontinuation.

 Weeks 4, 12, and 24 should be drawn pre-dosing. The precise PK sampling times relative to the actual dosing time must be accurately recorded on the eCRF. The date and time of sample collection must be recorded so that compliance with the sampling schedule can be confirmed.

PROTOCOL TITLE: ABATACEPT FOR THE TREATMENT OF PRIMARY  
BILIARY CIRRHOsis WITH AN INCOMPLETE BIOCHEMICAL RESPONSE TO  
URSODEOXYCHOLIC ACID

From the ICF:

The clinical study will be done only at UC Davis. The name and address of this study center and the investigator for this study center are listed on page 1 of this document. Authorized members of the study staff will do all study procedures.

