**Populations for Analyses**

The primary analysis set for efficacy and safety analyses will include all subjects who received at least one dose of study drug.

**PROTOCOL TITLE: ABATACEPT FOR THE TREATMENT OF PRIMARY BILIARY CIRRHOSIS WITH AN INCOMPLETE BIOCHEMICAL RESPONSE TO URSODEOXYCHOLIC ACID**

**Pharmacokinetic Analysis Population:** All available plasma concentration data from subjects who receive at least 1 dose of study medication and have at least 1 concentration result will be reported. However, only subjects without dose interruption will be included in the summary statistics.

**Immunogenicity Analysis Population:** For immunogenicity samples, included all subjects who receive at least 1 dose of abatacept and have at least 1 immunogenicity result reported.

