### **Analyses**

Endpoints of efficacy will be compared between Day 0 and Week 24 using paired t-test (or Wilcoxon signed rank test as indicated) for continuous variables and Chi-square test

PROTOCOL TITLE: ABATACEPT FOR THE TREATMENT OF PRIMARY  
BILIARY CIRRHOSIS WITH AN INCOMPLETE BIOCHEMICAL RESPONSE TO  
URSODEOXYCHOLIC ACID

(or Fisher's exact test) for categorical variables. For variables measured at multiple time points, Repeated Measures ANOVA will be employed. All analyses will be two-tailed and P values less than 0.05 will be considered as statistically significant.

The primary endpoint assessment will be the biochemical response rate defined by normalization of alkaline phosphatase or decrease of alkaline phosphatase by > 40% of the Day 0 level at 24 weeks of treatment. We will report the observed biochemical response rate and a 95% confidence interval for the expected biochemical response rate.

We will assess each of the secondary endpoints: absolute and percent change in alkaline phosphatase, absolute and percent change in alanine transferase (ALT), change in liver stiffness as measured by magnetic resonance elastography, change in quality of life measured by change in PBC-40, change in AMA titer, change in IgM level, and change in CD4+CD44+CD62L- and CD8+CD44+CD62L- frequencies in PBMC from Day 0 to week 24 by paired t-test or Wilcoxon signed-rank test when appropriate. Because these endpoints will be generated with these studies, to solve the problem of the above multiple significance testing, we will use the false discovery rate proposed by Benjamini and Hochberg. In addition, PK and immunogenicity of abatacept in patients with PBC will be estimated.

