## 16) Withdrawal of Subjects

### ***Discontinuation of Subjects from Treatment***

Subjects MUST discontinue investigational product (and noninvestigational product at the discretion of the investigator) for any of the following reasons:

- Withdrawal of informed consent (subject's decision to withdraw for any reason).
- Any clinical adverse event, laboratory abnormality, or intercurrent illness which, in the opinion of the investigator, indicates that continued participation in the study is not in the best interest of the subject.
- Pregnancy
  - Instruct WOCBP to contact the investigator or study staff immediately if they suspect they might be pregnant (eg, missed or late menstrual period) at any time during study participation. Institutional policy and local regulations should determine the frequency of on-study pregnancy tests for WOCBP enrolled in the study.
  - The investigator must immediately notify BMS if a study subject becomes pregnant.
- Loss of ability to freely provide consent through imprisonment or involuntary incarceration for treatment of either a psychiatric or physical (eg, infectious disease) illness.

All subjects who discontinue should comply with protocol-specified follow-up procedures. The only exception to this requirement is when a subject withdraws consent for all study procedures or loses the ability to consent freely (ie, is imprisoned or involuntarily incarcerated for the treatment of either a psychiatric or physical illness). If a subject withdraws before completing the study, the reason for withdrawal must be documented appropriately.

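### Subjects who leave the study before Week 24 have no PBC-40 after baseline, so the paired quality-of-life test cannot use them although the efficacy set is everyone dosed

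*Combined protocol and SAP*

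**What the plan says.** Quality of life is a secondary objective. Section 11, Study Endpoints, defines the endpoint as "Change in quality of life measured by change in PBC-40 from Day 0 to week 24". Under Analyses, the secondary endpoints are tested "from Day 0 to week 24 by paired t-test or Wilcoxon signed-rank test when appropriate".

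The Time and Events Schedule marks PBC-40 at the Pre-Treatment Visit and at Week 24, and nowhere else. Footnote 1 sits on the Week 36 column header and reads "Also to be performed for any subjects discontinuing the study with documentation for reason for discontinuation", which makes that column the exit visit. It contains vital signs, adverse events, chemistry, blood count, INR, CRP, AMA, immunoglobulins, ANA, lipids, the CD44+CD62L- measurement and PK/immunogenicity samples. The PBC-40 cell is blank.

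Populations for Analyses states: "The primary analysis set for efficacy and safety analyses will include all subjects who received at least one dose of study drug".

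Section 16, under Discontinuation of Subjects from Treatment, adds: "All subjects who discontinue should comply with protocol-specified follow-up procedures". It continues: "The only exception to this requirement is when a subject withdraws consent for all study procedures or loses the ability to consent freely". It does not name the visits that make up this follow-up.

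**The concern.** Both planned tests work on within-subject differences, so each subject needs a baseline score and a later one. The laboratory endpoints have values at several on-treatment visits and at the exit visit. PBC-40 has one post-baseline occasion. A subject who has left by then contributes nothing, and no later analysis can supply an answer that was never asked for.

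Section 16 ends treatment for adverse events, laboratory abnormalities or intercurrent illness when the investigator judges that continuing is not in the subject's interest. Departures of that kind could plausibly go with poorer quality of life. The trial is open-label with one arm, so there is no control group in which similar losses might offset the effect. If leaving is related to how subjects feel, the mean change among those who reach Week 24 is more favourable than the mean over everyone dosed.

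**Working it through.** **1. The plan's own figures.** No sample size or precision is stated for PBC-40. The only calculation, under Sample Size Determination, concerns the alkaline phosphatase response in 20 subjects, and it reproduces by exact binomial:

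- P(3 or fewer responders | n = 20, rate 5%) = 98.4% (stated as more than 98%).
- P(4 or more responders | n = 20, rate 30%) = 89.3% (stated as 89%).

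Neither figure involves PBC-40.

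**2. Who has a usable pair.** Reading the schedule, footnote 1 and section 16 together:

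| Subject | PBC-40 after baseline | Enters the paired test |
|---|---|---|
| Reaches Week 24, including those who leave between Weeks 24 and 36 | Week 24 | Yes |
| Stops drug, stays in follow-up | Week 24, if that visit is attended; the text does not say | Unsettled |
| Leaves the study before Week 24, attends the exit visit | None | No |
| Withdraws consent for all procedures, or can no longer consent freely, before Week 24 | None | No, under any schedule |

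The third row is the gap that the schedule creates and can close. The second needs one clarifying sentence.

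The mark for footnote 1 also appears on the pregnancy-test row. This does not alter the result: if the footnote applied only there, no exit visit would be defined and PBC-40 would still not be collected.

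**3. Possible bias (illustration).** Let p be the proportion of dosed subjects without a Week 24 score, and d the amount by which their mean change would be worse than that of the others, in SDs of the change score. The all-dosed mean is (1 - p) × (mean of those observed) + p × (mean of those lost). Hence:

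observed mean - all-dosed mean = p × d

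The documents give neither quantity. Assume p = 0.10 to 0.20 (2 to 4 of 20) and d = 0.5 to 1.0:

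- 0.10 × 0.5 = 0.05 SD
- 0.10 × 1.0 = 0.10 SD
- 0.20 × 0.5 = 0.10 SD
- 0.20 × 1.0 = 0.20 SD

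The standard error of a mean change is 1/√18 = 0.236 SD with 18 pairs and 1/√16 = 0.25 SD with 16. The bias then runs from 0.05/0.236 = 0.2 to 0.20/0.25 = 0.8 standard errors.

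**4. Loss of precision (illustration).** Two-sided paired t-test, alpha 0.05, noncentral t, before any false-discovery-rate adjustment:

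| Pairs | Change detectable with 80% power | Power for a 0.66 SD change |
|---|---|---|
| 20 | 0.66 SD | 80% |
| 18 | 0.70 SD | 75% |
| 16 | 0.75 SD | 69% |
| 14 | 0.81 SD | 63% |

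The numbers of pairs and the 0.66 SD effect are chosen for illustration.

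**The case against.** A reader might infer that everyone who stops early is dropped from the quality-of-life analysis. The documents do not support this. Footnote 1 concerns leaving the study. Section 16 keeps those who discontinue in protocol-specified follow-up, so a subject who only stops abatacept may still attend Week 24 and complete the survey. A subject who leaves after Week 24 already has the score.

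A reader might also infer that the plan contradicts itself by declaring an all-dosed set and then excluding people from it. It does not go that far. An analysis set says who is eligible; it does not promise that every endpoint is observed in everyone. Nothing says that leavers are excluded. Their absence follows from the paired tests and the lack of a missing-data rule in the text available, parts of which were removed from the public file and could bear on follow-up.

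Three further objections carry weight. The size rests wholly on assumed inputs, and the direction is plausible rather than shown. An exit score from, say, Week 4 is not a Week 24 score, and using it as such in the main analysis would resemble carrying the last observation forward. The stakes are modest: PBC-40 is one of several secondary endpoints under false-discovery-rate control, and the case for a randomised trial rests on the responder count.

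What survives is that a subject who leaves before Week 24 has no scheduled way to give a second PBC-40, even when attending an exit visit. MR elastography has the same pattern ("MR Elastography X X", pre-treatment and Week 24), but it is a heavier procedure, and the change proposed here is confined to the survey.

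**Conclusion.** The point holds for subjects who leave the study before Week 24. They have no PBC-40 after baseline and cannot enter the paired test, and the available text gives no rule that reconciles this with an efficacy set that "will include all subjects who received at least one dose of study drug". For subjects who stop drug but stay in follow-up, the documents leave the matter open.

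The size is unknown. The 0.05-0.20 SD above is an illustration that assumes 10-20% without a Week 24 score and a change worse by 0.5-1.0 SD in those subjects. It is not an estimate, and if leaving is unrelated to quality of life there is no bias, only the loss of pairs. The point is minor but worth acting on, because the information must be collected at the time or not at all.

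**What to change.** 1. Add PBC-40 to the assessments made at early discontinuation. Because the Week 36 column doubles as the exit visit, use a separate early-discontinuation column or a footnote on the PBC-40 row; a plain mark in the Week 36 column would also add the survey for every completer.
2. State in the schedule and in section 16 that subjects who stop drug but remain in follow-up complete PBC-40 at Week 24.
3. Under Analyses, keep the observed Day 0 to Week 24 change as the main PBC-40 analysis, and report how many dosed subjects it includes.
4. Add a sensitivity analysis in all dosed subjects with a post-baseline score, using the exit score where Week 24 is missing, and list the week at which each exit score was taken.

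The cost is a schedule entry, a few sentences and a few minutes for each subject who leaves, at a visit already required. Exit scores will come at varying times before Week 24, which is why they belong in the sensitivity analysis. The change does not help with subjects who withdraw consent for all procedures.
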